N	Number (typically refers to number of subjects/sample size)
NIAID	National Institute of Allergy and Infectious Diseases
NIH	National Institutes of Health
NSAID	nonsteroidal anti-inflammatory drugs
OHRP	Office for Human Research Protections
PBMC	Peripheral Mononuclear Cells
PCR	Polymerase Chain Reaction
PI	Principal Investigator
RCHSPB	Regulatory Compliance and Human Subjects Protection Branch
RNA	Ribonucleic Acid
SAE	Serious Adverse Event
sTF	soluable tissue factor

SVR	Sustained virologic response
ULN	Upper Limit of Normal
UP	Unanticipated Problem
UPnonAE	Unanticipated Problem that is not an Adverse Event

PROTOCOL SUMMARY

Full Title:	Elite Controller and ART-treated HIV+ Statin versus ASA Treatment Intervention Study (ECSTATIN)
Short Title:	Immune Activation in Elite Controllers
Clinical Phase:	Phase 1
Protocol	14-I-0039
Conducted by:	NIAID-DIR
Principal Investigator:	[name].
Sample Size:	N=80 Elite Controller (EC) Group: N=40 Randomization arms: aspirin (ASA): N=20 atorvastatin (ATV): N=20 Treated Progressor Group (ART<50): N=40 Randomization arms: ASA: N=20 ATV: N=20
Accrual Ceiling:	N=120
Study Population:	Subjects (≥ 18 years) infected with the human immunodeficiency virus type 1 (HIV-1) grouped ECs (no opportunistic infections [OIs], no antiretroviral therapy [ART], stable CD4 T cell counts greater than 3 years, HIV-RNA less than the lower limit of detection (LLD) of commercially available assays) OR on continuous combination ART ≥ 4 years with HIV-RNA less than the lower limit of detection (LLD) of commercially available assays). Transient measurements of detectable viremia, or “blips,” are allowed, if flanked by viral loads less than the lower limit of detection.
Accrual Period:	4 Years
Study Design:	This is an open-label, randomized controlled trial intended to study potential modifiers of immune activation in HIV-1 infected ECs (no OIs, no ART, stable CD4 T cell counts greater than 3 years, viral load less than the LLD of the assay used) (EC group) and treated progressors on continuous combination ART for ≥ 4 years with HIV-RNA below the limit of detection in commercially available assays (<40, <48, or <50 copies/mL, depending on the assay used) for greater than 3 years (ART <50 group). After screening at

either Hennepin County Medical Center or the NIH Clinical Center, subjects will be enrolled on study at the NIH Clinical Center and will enter a 3 month observation period (to establish baseline values for biomarkers/cellular markers). At Month 3, participants will be randomized within each group to receive once daily oral dose of ASA 81 mg or ATV 40 mg (dose adjusted for subjects on antiretroviral regimens with significant interactions, see Section 5.3.1) and will be treated for 9 months, followed by 3 months of discontinuation of study drug.

Study Duration:

Start Date: November 2013

End Date: November 2019

Study Agent/

Intervention Description:

- ASA, 81 mg, once daily, PO for 9 months
- ATV, 40 mg (dose adjusted for subjects on antiretroviral regimens with significant interactions, see Section 5.3.1), once daily, PO for 9 months

Primary Objective:

To evaluate changes from baseline in sCD14 after 9 months of treatment with ASA or ATV, in EC and Treated Progressor (ART <50) groups combined.

Secondary Objectives:

- To evaluate changes in soluble biomarkers including sCD14, IL-6, D-dimer, hsCRP, soluble tissue factor (sTF), sCD163 and other related markers of inflammation and coagulation in EC and ART <50 copies/mL groups treated with ASA or ATV with groups combined as well as independently within each group and arm, at 6, 9, and 12 months.
- To evaluate changes in T cell activation (measured by HLA-DR/CD38 co-expression), monocyte immune activation (measured by activated monocyte subsets expressing either CD14⁺⁺CD16⁺ and CD14^{var}CD16⁺ and markers of activation, CCR5 and TF, and migration, CCR2 and CX3CR1 and other relevant markers), at 6, 9, and 12 months.
- Assess if a 3-month wash out period (at Month 15) following 9 months of study drug results in biomarker and cellular activation changes.
- To compare changes of biomarkers and cellular markers between EC and ART <50 groups.
- To compare changes of biomarkers and cellular markers between ASA and ATV arms of each group and in both groups combined.

- To evaluate changes in plasma viral load, as measured by single copy assay in EC and ART <50 groups treated with ASA or ATV from baseline, to months 3 and 12.
- Assess tolerance of ASA and ATV treatment for 6 months in HIV+ participants without clinical indication for these drugs.
- Assess prevalent atherosclerotic disease in EC vs ART <50 groups by MR imaging of carotids at baseline.
- Assess changes in MR imaging of carotids after 9 months of ASA or ATV in EC or ART <50 groups, and both groups combined.
- Correlate MR vascular imaging with soluble and cellular biomarkers of inflammation.
- To assess in an exploratory study the microbiome of EC versus ART<50 groups and the possible influence of ASA or statin therapy

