In the current 2 group, randomized, open label trial, we intend to study the effects of a lipid lowering agent vs aspirin (ASA) on immune activation in HIV-1 infected participants. One group will consist of ECs who are HIV-1 infected, maintain HIV-RNA levels less than the LLD of commercially available assays in the absence of ART, have no history of ART or opportunistic infections (OIs) and have stable CD4 T cell counts for greater than 3 years. The second group will enroll HIV-1 infected Treated Progressors (henceforth referred to as ART <50) who have maintained HIV-RNA below the limit of detection in commercially available assays (<40, <48, or <50 copies/mL) for greater than 3 years on ART (treatment duration greater than 4 years). Up to 2 months after the screening and enrollment visit, each group will enter a 3 month observation period (to establish baseline values for biomarkers/cellular markers). After 3 months, participants from each group will be randomized to either ASA, 81 mg PO daily, or atorvastatin (ATV), 40 mg (dose adjusted for subjects on antiretroviral regimens with significant interactions, see Section 5.3.1), and will be treated for 9 months, followed by 3 months of a wash out period (see Figure 1). The primary end point will be change of sCD14 after 9 months of study intervention from Month 3 to Month 12 in each treatment arm, with groups combined (EC and ART <50). Secondary objectives will be to compare changes in soluble biomarkers (sCD14, IL-6, D-dimer, hsCRP, sTF, sCD163 and other relevant markers of inflammation and coagulation) and cellular activation markers between study groups and treatment arms (ASA vs statin and EC vs ART<50 and with groups combined), to evaluate cardiovascular (CV) disease prevalence in EC vs ART <50 by MR imaging of carotids, to determine MR measurements and correlations with biomarkers and cellular activation markers, and to investigate changes in plasma viremia as measured by single copy assay over time.

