3.2 Secondary Objectives

- Compare changes in soluble biomarkers (sCD14, IL-6, D-dimer, hsCRP, sTF, sCD163 and other relevant markers of inflammation and coagulation) and cellular activation markers between study groups and treatment arms (ASA vs statin and EC vs ART<50 and with groups combined) at 6, 9, 12 months, and after 3 month washout at 15 months. Comparisons between EC and ART<50 will be adjusted for CD4, smoking status and age.
- Evaluate cardiovascular (CV) disease prevalence in EC vs ART <50 by MR imaging of carotids at baseline and follow how it changes over time
- Determine MR measurements and correlations with biomarkers and cellular activation markers
- Investigate changes in plasma viremia as measured by single copy assay
- To assess in an exploratory study the microbiome of EC versus ART<50 groups and the possible influence of ASA or statin therapy
-

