3.4.2 Secondary Endpoints

- To evaluate changes in soluble biomarkers (sCD14, IL-6, D-dimer, hsCRP, sCD163, sTF as well as other relevant markers of inflammation and coagulation) in EC and ART <50 groups treated with ASA or ATV, independently within each group and arm and with groups combined, at 6, 9, and 12 months.
- To evaluate changes in T cell activation (measured by HLA-DR/CD38 co-expression), monocyte immune activation (measured by activated monocyte subsets expressing either CD14⁺⁺CD16⁺ and CD14^{var}CD16⁺ and markers of activation, CCR5 and TF, and migration, CCR2 and CX3CR1), at 6, 9, 12 months of study.
- To investigate differences in HLA type, which has been implicated as a mechanism of viremic control in ECs, between groups and treatment arms, as it relates to treatment response.
- Assess if a wash out period following 9 months of therapy results in biomarker and cellular activation changes after 3 months (Month 15).
- To compare changes of biomarkers and cellular markers between EC and ART <50 groups after adjusting for smoking, CD4 counts and age.
- To compare changes of biomarkers and cellular markers between ATV and ASA arms of each group and in both groups combined.
- To evaluate changes in plasma viral load, as measured by single copy assay in EC and ART <50 groups treated with ASA or ATV at baseline, 3 and 12 months.
- Assess toxicity profile of ASA versus ATV in the study population.
- Assess prevalent atherosclerotic disease in EC vs ART<50 by MR imaging of carotids.
- Assess changes in MR imaging of carotids after 9 months of statin or ASA in each group and both groups combined.
- Correlate MR vascular imaging with soluble and cellular biomarkers of inflammation.

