6.3 Randomization

The NIH Pharmacy Department will carry out blocked, open-label, randomization using a random number generator. At the Month 3 study visit, ECs and Treated Progressors will be separately randomized 1:1 to open label ASA or ATV arms.

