13.5 Efficacy Analysis

The primary endpoint will be set as a change in sCD14 after 9 months of treatment with ASA or ATV, in ECs and in Treated Progressors (ART <50) combined. Assuming 40 patients enroll in each treatment arm, with a mean sCD14 of 2.45 µg/mL and a standard deviation of 0.45 µg/mL, the study has 95% power to detect a reduction of 0.20 in sCD14 levels (See Section 13.2) after 9 months of treatment. The significance of paired differences within each group will be evaluated using two-sided nonparametric (one-sample signed rank) test. As discussed above, this power decreases to 74% when treatment arms are compared individually within each group (as a secondary endpoint, see below). Adjustment for differences in CD4, age and smoking status will be done in any between group (EC vs ART<50) comparisons.

Secondary endpoints, including group comparisons (ASA vs statin and EC vs ART<50) of changes in biomarkers and T cell activation, cardiovascular disease prevalence, and changes in plasma viremia will be evaluated using two-sided nonparametric (Wilcoxon rank-sum) tests. Exploratory analyses comparing paired differences of carotid IMT thickness at Month 0 and Month 12 within each group will be assessed by two-sided nonparametric (one-sample signed rank) tests. Associations between continuous variables (MR measurements and biomarkers and cellular activation markers) will be assessed using Spearman rank order correlation coefficients. Linear regression models will be used to control for factors such as age, smoking, and inflammatory biomarkers. For all evaluations, type I error will be set at 0.05.

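### The only stated contrast for single-copy viremia runs from Month 0 to Months 3 and 12, although drug is taken only from Month 3 to Month 12; the fully on-drug change is not defined

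*Combined protocol and SAP*

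**What the plan says.** Five places address plasma viremia by single copy assay.

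- **Protocol Summary, Secondary Objectives:** the objective opens "To evaluate changes in plasma viral load, as measured by single copy assay in EC and ART <50 groups treated with ASA or ATV from" and its visits are given in the words "groups treated with ASA or ATV from baseline, to months 3 and 12". This is the only statement that names both a reference visit and outcome visits.
- **Section 3.4.2:** the endpoint is assessed in "groups treated with ASA or ATV at baseline, 3 and 12 months". This lists three visits and does not say which is the reference.
- **Section 3.2:** "Investigate changes in plasma viremia as measured by single copy assay", with no visits.
- **Précis (Section 1):** "to investigate changes in plasma viremia as measured by single copy assay over time", with no contrast.
- **Section 13.5:** "changes in plasma viremia will be evaluated using two-sided nonparametric (Wilcoxon rank-sum) tests", with no interval.

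On timing, Section 6.3 states: "At the Month 3 study visit, ECs and Treated Progressors will be separately randomized 1:1 to open label ASA or ATV arms". Section 6.4 starts study drug after that randomization, and Sections 3.3 and 6.6 end it at Month 12. Section 6.2 and Appendices B and C give the name baseline to Month 0. For comparison, Section 3.4.1 fixes the primary sCD14 change as Month 3 to Month 12.

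**The concern.** The objective is worded as a change in groups treated with ASA or ATV. Of the two changes it names, one ends at the visit where participants are randomized and first receive drug, and the other begins three months before that visit. An analyst who follows the Protocol Summary would report a pre-randomization change under a treatment label, and a Month 12 change that mixes untreated with treated time. An analyst who follows Section 3.4.2 could choose among three intervals, in an open-label trial, with no rule to decide.

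The issue is what the viremia result can be taken to mean. Within an arm, or between EC and ART<50, movement during the observation period could be read as part of a response to drug.

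**Working it through.** The documents give no power, sample size or variability for viremia, so there is no stated figure to reproduce. The check is interval arithmetic followed by simple algebra.

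**1. Which visit is baseline.** Section 6.2 and the appendices use the word for Month 0. In this objective it cannot mean Month 3, since a change from Month 3 to Month 3 is zero by definition.

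**2. Months on drug in each interval.** Drug runs from Month 3 to Month 12. For an interval from a to b, months on drug = max(0, min(b, 12) − max(a, 3)). Visits are taken at their nominal times; the windows are ± 2 weeks.

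| Interval | On drug (months) | Untreated (months) | Untreated share | Stated for viremia? |
|---|---|---|---|---|
| Month 0 to 3 | 0 | 3 | 3/3 = 100% | Yes, Protocol Summary |
| Month 0 to 12 | 12 − 3 = 9 | 3 | 3/12 = 25% | Yes, Protocol Summary |
| Month 3 to 12 | 12 − 3 = 9 | 0 | 0% | No |

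**3. Are the samples there?** Appendix C lists 27 mL for the assay three times. The daily totals confirm the visits. Months 3 and 12 total 141.5 mL against 114.5 mL at Months 6, 9 and 15, a difference of 27 mL. The Month 0 items add to the stated 146.5 mL only with the 27 mL included: 3 + 4.5 + 8 + 4 + 6 + 3 + 10 + 55 + 12 + 8 + 27 + 6. The Month 3 to 12 change can therefore be computed from samples already planned.

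**4. What each change estimates.** Suppose, for illustration, an untreated drift of d per month in a group and a drug effect of e by Month 12.

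- Month 0 to 3: 3d
- Month 0 to 12: 12d + e
- Month 3 to 12: 9d + e

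*Within an arm:* starting at Month 0 adds 3d of pre-drug movement. Starting at Month 3 removes that part but not the 9d that runs alongside treatment. Without an untreated arm, no choice of reference visit removes that.

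*EC versus ART<50:* the drifts may differ, because the groups are not randomized. Starting at Month 0 adds 3 × (d in EC − d in ART<50) to the contrast.

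*ASA versus ATV:* with a common drift, d cancels, and both Month 0 to 12 and Month 3 to 12 estimate e(ASA) − e(ATV). Over Month 0 to 3 the expected difference is zero.

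**5. Precision of ASA versus ATV.** With equal variance s² at each visit and within-person correlation r, the variance of a change is 2s²(1 − r). If r is the same over 9 and 12 months, the two intervals are equally precise. If r falls with time, the 12-month change is noisier. The documents do not give s or r for single-copy values, so this cost cannot be quantified. The SD of 0.45 µg/mL and correlation of 0.71 in Section 13.2 are for sCD14 and cannot stand in for viremia.

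**The case against.** The strongest reply is that this is one loosely worded summary line. Section 3.4.2, which defines the endpoints, only lists visits, and nothing there or in Section 3.2, the Précis or Section 13.5 excludes a Month 3 to 12 change. The primary objective also speaks of change from baseline, and Section 3.4.1 resolves it to Month 3 to Month 12. Two pre-drug samples and one at the end of treatment also suit a design whose observation period exists to establish baseline values.

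Much of this stands. A reader might infer that the plan has ruled out the on-drug contrast; it has not. But the resolution made for sCD14 is not made for viremia, and the one contrast that is stated cannot be read that way. Using Month 0 to 3 as a run-in comparison would be sensible, but no section says so for viremia.

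Three further inferences are tempting and not supported:

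- **That any significant Month 0 to 3 change is a false positive.** Within a group, or between EC and ART<50, it may be real untreated movement. The error would be to attribute it to a drug. Nor does any section say that the arms will be compared over that interval.
- **That the ASA versus ATV comparison is biased.** Common drift cancels there.
- **That a loss of power can be stated.** That would need single-copy variability and correlation, which the documents do not give. Section 13.5 also assigns group comparisons of viremia to a rank-sum test, so a one-sample calculation on sCD14 inputs would not describe the planned analysis.

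**Conclusion.** The concern holds as a defect in the definition of one secondary objective. Of the two stated viremia changes, one has no drug exposure and the other is 25% untreated, while the only fully on-drug change is not defined. The consequence falls on the within-arm changes and the EC versus ART<50 comparison, which pre-drug drift can enter. For ASA versus ATV the only possible cost is some precision, if within-person correlation falls with time.

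This rests on nominal visit times and on the Month 3 assay sample being drawn before the first dose. Section 6.4 specifies that order for leukapheresis only, but exposure on the same visit day would be negligible. The effect on viremia results cannot be sized from the documents. The severity is minor to moderate: data collection is adequate, and the primary sCD14 endpoint is untouched.

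**What to change.** In the Protocol Summary, Section 3.4.2 and Section 13.5, define the treatment change in single-copy viremia as Month 3 to Month 12, for the within-arm, ASA versus ATV, and EC versus ART<50 analyses. State that Month 0 to Month 3 will be reported descriptively by HIV group as untreated background variation, not as an effect of ASA or ATV. Bring Section 3.2 and the Précis into line.

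The cost is wording in these five places. The samples are already scheduled at Months 0, 3 and 12, so no sample, visit or assay is added. The change does not remove drift during treatment from the within-arm results, and the report should say so.

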1 PRÉCIS

Despite dramatic improvements in mortality with antiretroviral therapy (ART), HIV-infected persons remain at risk of developing non-infectious complications, including cardiovascular, renal, and neurological disease. A small subset of the HIV-infected population achieve durable control of HIV virus in the absence of ART. These individuals, termed elite controllers (ECs), remain ART naïve, have stable CD4 T cell counts for many years and have no history of opportunistic infections. Despite the lack of AIDS complications, recent evidence suggests ECs may exhibit heightened immune activation that may contribute to a potentially increased risk for non-infectious complications, similar to successfully treated progressors.

In the current 2 group, randomized, open label trial, we intend to study the effects of a lipid lowering agent vs aspirin (ASA) on immune activation in HIV-1 infected participants. One group will consist of ECs who are HIV-1 infected, maintain HIV-RNA levels less than the LLD of commercially available assays in the absence of ART, have no history of ART or opportunistic infections (OIs) and have stable CD4 T cell counts for greater than 3 years. The second group will enroll HIV-1 infected Treated Progressors (henceforth referred to as ART <50) who have maintained HIV-RNA below the limit of detection in commercially available assays (<40, <48, or <50 copies/mL) for greater than 3 years on ART (treatment duration greater than 4 years). Up to 2 months after the screening and enrollment visit, each group will enter a 3 month observation period (to establish baseline values for biomarkers/cellular markers). After 3 months, participants from each group will be randomized to either ASA, 81 mg PO daily, or atorvastatin (ATV), 40 mg (dose adjusted for subjects on antiretroviral regimens with significant interactions, see Section 5.3.1), and will be treated for 9 months, followed by 3 months of a wash out period (see Figure 1). The primary end point will be change of sCD14 after 9 months of study intervention from Month 3 to Month 12 in each treatment arm, with groups combined (EC and ART <50). Secondary objectives will be to compare changes in soluble biomarkers (sCD14, IL-6, D-dimer, hsCRP, sTF, sCD163 and other relevant markers of inflammation and coagulation) and cellular activation markers between study groups and treatment arms (ASA vs statin and EC vs ART<50 and with groups combined), to evaluate cardiovascular (CV) disease prevalence in EC vs ART <50 by MR imaging of carotids, to determine MR measurements and correlations with biomarkers and cellular activation markers, and to investigate changes in plasma viremia as measured by single copy assay over time.

2 BACKGROUND INFORMATION AND SCIENTIFIC RATIONALE

2.1 Background Information

2.1.1 Immune Activation in HIV-infected Persons

HIV-infected individuals are currently at increased risk for non-infectious complications, including cardiovascular, renal and hepatic disease, bone loss and neurocognitive impairment, despite decreased risk of AIDS due to the development of ART [1, 2]. Biomarkers linked to non-AIDS complications (venous thromboembolism, cardiovascular disease and renal disease) including D-dimer, soluble (s) tissue factor (TF), sCD14, C-reactive protein (CRP), and proinflammatory cytokines have been observed at higher levels in HIV seropositive compared to seronegative persons [3-7]. Furthermore, elevated levels of biomarkers associated with inflammation, coagulation and monocyte activation (D-dimer, CRP, IL-6, and sCD14) have been found to be independent predictors of all-cause mortality and increased risk of AIDS [8-10]. Even in the presence of ART-induced viral suppression, HIV-infected individuals remain at a heightened risk of atherosclerotic disease and increased carotid intima-media thickness (IMT) and show increased inflammation and monocyte activation [11, 12] [13]. In HIV-negative subjects, the CD14⁺⁺CD16⁺ activated monocyte phenotype independently predicts cardiovascular disease [14]. Monocytes are known to migrate to developing atherosclerotic plaques by chemotaxis and differentiate into macrophages on site. Macrophage activation leads to the production of oxygen radicals, inflammatory cytokines, and chemokines, ultimately causing deleterious tissue damage and increased inflammation [15].

